10.2.2 Analysis of Long-Term Adverse Event Rates

Long-term adverse event rates for upadacitinib 15 mg QD will be analyzed using event rates adjusted by cumulative exposure. This includes TEAEs occurred under upadacitinib 15 mg QD exposure from subjects starting on upadacitinib 15 mg QD and subjects switching from placebo to upadacitinib 15 mg QD.

For this event rate calculation, 1 year will be considered to be 365.25 days. For each treatment group, the numerator of the overall rate will be the total number of TEAEs reported for the event; that is, a subject can contribute more than one event to the numerator. The denominator of the rates will be the total number of days exposed to upadacitinib 15 mg QD summed across all treated subjects divided by 365.25. The TEAE

rate per 100 patient-years of exposure will be calculated as $([\text{numerator}/\text{denominator}]) * 100$. The number of TEAEs reported (numerator), the total number of years of study drug exposure (denominator), and the TEAE rate per 100 patient-years will be presented for each treatment group.

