Safety data are available from the two Phase 2 studies (N = 575) which showed that the types and frequencies of AEs during upadacitinib treatment were consistent with subjects with moderately to severely active RA receiving immunomodulatory therapy. The incidences of AEs were numerically higher in the upadacitinib dose groups, with a trend toward higher rates with higher doses of upadacitinib. The most frequently reported AEs ( $\geq 5\%$ ) in the upadacitinib treated subjects were urinary tract infection, headache, upper respiratory tract infection, and nausea. There were 6 subjects (1.3% of total combined populations) with herpes zoster reactivation distributed across the upadacitinib dose groups, and 2 subjects (1.9%) in the placebo groups. In these two 12 week studies, a total of 2 subjects in the upadacitinib treatment groups reported malignancies. One subject reported non-melanoma skin cancers (NMSC) (basal cell and squamous cell carcinoma) and 1 subject was diagnosed with lung cancer after the final scheduled visit, and subsequently died 14 weeks after study completion. These events were reported by the Investigators as not possibly related to study drug. Elevations of liver function tests were sporadic with no clear dose-response relationship observed. As observed with other JAK inhibitors, treatment with upadacitinib resulted in an increase in lipids (low-density lipoprotein cholesterol [LDL-C] and high density lipoprotein cholesterol [HDL-C]). Among subjects with laboratory evidence of systemic inflammation (as evidenced by high-sensitivity C-reactive protein [hsCRP]  $>$  upper limit of normal [ULN]), treatment with lower doses of upadacitinib (3 mg BID and 6 mg BID) was associated with improvements in mean hemoglobin relative to placebo. At higher doses, there was a reduction in mean hemoglobin; however, the mean hemoglobin levels remained within normal range throughout the treatment period.

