10.2.1.1 Adverse Events Overview

The number and percentage of subjects experiencing TEAEs will be summarized by "as treated" treatment group for the following AE categories.

- All TEAEs
- Treatment-emergent serious adverse events (SAEs)
- Treatment-emergent severe adverse events
- TEAEs reasonably possibly related to study drug
- TEAEs of special interest
- TEAEs leading to discontinuation of study drug
- TEAE leading to death

Additional AEs may be considered for tabulation/summary based on recommendations from Clinical and Safety as deemed appropriate.

For TEAEs of special interest, the point estimate and 95% CI (using normal approximation and separate group variance) will be provided for the treatment difference in AE percentage between upadacitinib group and the placebo group.

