10.2.2.1 Overview of Adverse Events Rates per 100 Patient-Years of Study Drug Exposure

An overview of AEs per 100 patient-years of study exposure will be presented for upadacitinib 15 mg QD for the following AE categories.

- All TEAEs
- Treatment-emergent serious adverse events (SAEs)
- Treatment-emergent severe adverse events
- TEAEs reasonably possibly related to study drug
- TEAEs of special interest
- TEAEs leading to discontinuation of study drug
- TEAE leading to death

Additional AEs may be considered for tabulation/summary based on recommendations from Clinical and Safety as deemed appropriate.

10.2.2.2 Adverse Events Rates per 100 Patient-Years of Study Drug Exposure by SOC and PT

For upadacitinib 15 mg QD treatment group, the TEAE rate per 100 patient-years of exposure as outlined in Section 10.2.2 will be calculated overall, for each SOC and each PT, for each of the following events:

- All TEAEs
- Treatment-emergent serious adverse events (SAEs)
- Treatment-emergent severe adverse events
- TEAEs reasonably possibly related to study drug

- TEAEs leading to discontinuation of study drug
- TEAE leading to death

**10.2.2.3 Adverse Events of Special Interest Rates per
100 Patient-Years of Study Drug Exposure**

The Adverse Events of Special Interest (AESI) rate per 100 patient-years of exposure as outlined in Section 10.2.2 will be calculated overall, for each SOC and each PT, for each of the AESI listed in Section 10.2.1.6.

**10.2.2.4 Listing of Serious Adverse Events (Including Deaths) and
Adverse Events Leading to Study Drug Discontinuation**

All serious adverse events (SAEs), deaths, and adverse events leading to discontinuation of study drug will be listed.

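### The SAP's long-term AE and AESI rate tables count events only, with no number of patients affected and no confidence interval

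*SAP*

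**What the plan says.** SAP 10.2.2 defines the long-term rate for upadacitinib 15 mg. The numerator is every treatment-emergent event, and "a subject can contribute more than one event to the numerator". The denominator is the "total number of days exposed to upadacitinib 15 mg QD summed across all treated subjects divided by 365.25". The quantities to be displayed are the "number of TEAEs reported (numerator), the total number of years of study drug exposure (denominator), and the TEAE rate per 100 patient-years". Sections 10.2.2.1 and 10.2.2.2 apply this to the overview and to the SOC and PT tables. Under 10.2.2.3 the AESI rate "will be calculated overall, for each SOC and each PT, for each of the AESI listed in Section 10.2.1.6". None of these sections specifies a count of subjects or an interval.

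Other parts of the documents bear on the point:

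- Protocol 6.1.1.1 has a reported AE that worsens in severity entered as a new AE.
- Protocol 8.1.5.2 applies its AE conventions, by default, to Period 1 and to the combined Period 1 and 2 analysis. Section 8.1.5.2.1 then plans numbers and percentages of subjects for the general categories, including SAEs, discontinuations due to AEs and death. It says that AESIs will be summarised, without naming the statistic, and that their event rate will be given in addition for the combined analysis.
- SAP 10.1 plans a long-term listing of subjects with TEAEs, and 10.2.2.4 plans listings of SAEs, deaths and AEs leading to discontinuation.
- SAP 10.2.1.1 gives Period 1 AESIs as subject percentages, and "the point estimate and 95% CI (using normal approximation and separate group variance) will be provided" for the difference between arms.
- SAP 9.1.1 and 9.3 give confidence intervals for long-term efficacy although nothing there is tested. SAP 10.3.3.2 gives the number and percentage of subjects for long-term laboratory abnormalities.

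**The concern.** Period 2 exists to evaluate long-term safety, tolerability and efficacy, and these rate tables are the main tabulated AE result for it. A reader will want to know how many patients had the event, and what risk a low or zero count rules out. The tables answer neither. An event count mixes the number of patients affected with how often each one had the event recorded, and the protocol's rule on worsening adds to the second part: one episode of neutropenia that worsens can enter the numerator twice. The Phase 2 summary in Protocol 3.0 offers another route, a single subject with both a basal cell and a squamous cell carcinoma.

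Without an interval, a rate of 0.0 or 0.3 per 100 patient-years can look more reassuring than exposure of this size allows.

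**Working it through.** The documents state no expected exposure, event count or precision for the long-term rates, so the plan has no figure to reproduce. The check asks what the planned display would show and what a subject-based display would show.

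**Inputs.** There are 161 subjects per arm (Protocol 8.3). Time on upadacitinib is 12 + 52 = 64 weeks (448 days) in Group 1 and 52 weeks (364 days) in Group 2 (Protocol synopsis). A year is 365.25 days (SAP 10.2.2). The 10% dropout in SAP 4.3 belongs to the efficacy sample size. Long-term loss of exposure is not given, so 0 to 30% is assumed.

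**Maximum exposure.** (161 × 448 + 161 × 364) / 365.25 = 130,732 / 365.25 = 357.9 patient-years (PY).

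**Exact Poisson 95% limits for k affected subjects.** Lower = χ²(0.025; 2k)/2 (zero when k = 0). Upper = χ²(0.975; 2k + 2)/2. Each is divided by PY and multiplied by 100. For k = 0 the upper limit on the count is 3.69, so the rate limit is 3.69 / 357.9 × 100 = 1.03.

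| Assumed exposure loss | PY | 0 subjects: upper limit | 1 subject: rate (95% CI) | 3 subjects: rate (95% CI) |
|---|---|---|---|---|
| 0% | 357.9 | 1.03 | 0.28 (0.01 to 1.56) | 0.84 (0.17 to 2.45) |
| 10% | 322.1 | 1.15 | 0.31 (0.01 to 1.73) | 0.93 (0.19 to 2.72) |
| 20% | 286.3 | 1.29 | 0.35 (0.01 to 1.95) | 1.05 (0.22 to 3.06) |
| 30% | 250.5 | 1.47 | 0.40 (0.01 to 2.22) | 1.20 (0.25 to 3.50) |

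The planned table at full exposure would print 3 events, 357.9 PY and 0.84 per 100 PY for three subjects with one event each, and the same line for one subject with three.

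**Effect of censoring at first event.** The table uses uncensored time. An affected subject can lose at most 448 / 365.25 = 1.23 PY, so three lose at most 3.68 PY, and 3 / (357.92 − 3.68) × 100 = 0.85 instead of 0.84. With counts this small, censoring moves rates and limits by about 1% at most.

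**Where recurrence matters.** Protocol 5.4.1 requires withdrawal for gastrointestinal perforation and for malignancy other than localised NMSC or cervical carcinoma in situ, and SAP 10.2 stops counting TEAEs 30 days after the last dose. Repeats of those events in one subject are therefore rare by design, and a death cannot recur. By contrast, Protocol 6.1.7 allows study drug to be resumed or continued, under stated conditions, after infections, cytopenias and CPK elevations. Recurrence is a practical issue mainly for infections, herpes zoster, cytopenias, CPK, hepatic events and NMSC. For the rarely recurring AESIs and for deaths, what is missing is the interval.

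**The case against.** The case for leaving the SAP alone is substantial. Events per patient-year is an accepted descriptive measure, and no test or decision depends on it. The protocol already plans subject counts for the combined analysis, and the SAP presents itself as elaborating the protocol. Listings will identify subjects, and for a rare AESI a glance at one separates one patient from three. SAP 7.0 also tabulates Period 2 subjects whose primary reason for stopping study drug was an AE. When the count is zero, a reader can derive the upper limit from the printed patient-years. The Period 1 interval is for a difference from placebo, which has no counterpart in a single-arm analysis.

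All of that stands, and it rules out three stronger readings that a reader might infer:

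- **The event rate is the only long-term AE statistic planned.** Protocol 8.1.5.2 and 8.1.5.2.1 plan subject numbers and percentages, and the listings are further output. The gap lies in the SAP's long-term section, which does not carry the protocol's counts forward.
- **Counting repeats is an error and the rate should be replaced.** It is a valid answer to a different question, and it should stay.
- **The plan's intervals would be too narrow under recurrence.** The SAP computes no interval on these rates, and the documents give no recurrence rate from which to size such a shortfall.

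The objection does not remove the rest. A listing gives neither an incidence rate nor an interval. The interval on the long-term AE rates is absent from both documents. A purely descriptive purpose does not explain that, since the equally untested long-term efficacy results do get intervals.

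**Conclusion.** The point holds as a reporting gap in SAP 10.2.2 to 10.2.2.3, and closing it is a cheap improvement, not the correction of a wrong method. As planned, the tables do not show how many patients had each event or how uncertain a low rate is. In the worked case the same printed 0.84 per 100 PY corresponds to a subject-based rate of 0.84 or 0.28, and a printed 0.0 is compatible with up to 1.03 per 100 PY at full exposure, or 1.15 to 1.47 if 10 to 30% of exposure is lost.

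These figures assume 161 subjects per arm and, for the 357.9 PY maximum, full treatment. The exposure losses and the counts of zero, one and three are illustrations, not forecasts. Nothing here affects the efficacy analyses or the Period 1 safety comparison.

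**What to change.** In SAP 10.2.2 to 10.2.2.3, keep events per 100 PY as defined. For each AESI, for SAEs and for AEs leading to discontinuation, add:

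- the number and percentage of subjects with at least one event while on upadacitinib;
- the incidence rate per 100 PY, with each affected subject's upadacitinib exposure censored at the first such event;
- an exact Poisson 95% CI on that incidence rate. The interval belongs on the subject-based rate because a Poisson interval on repeat events would ignore correlation within subjects.

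For deaths, add only the exact CI. State that the subject counts implement Protocol 8.1.5.2 and 8.1.5.2.1 for the combined analysis.

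The cost is a few lines of SAP text and some added table programming, using data already collected. The downside is a second rate column, which needs clear labelling so that event rates and first-event incidence rates are not confused.

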## **5.0 Investigational Plan**

### **5.1 Overall Study Design and Plan: Description**

This is a Phase 3 multicenter study that includes two periods. Period 1 is a 12-week, randomized, double-blind, parallel-group, placebo-controlled period designed to compare the safety and efficacy of upadacitinib 15 mg QD versus placebo for the treatment of signs and symptoms of subjects from China and selected countries including Brazil and South Korea with moderately to severely active RA who are on a stable dose of csDMARDs and have an inadequate response to csDMARDs. Period 2 is an open-label 52-week extension period to evaluate the long-term safety, tolerability, and efficacy of upadacitinib 15 mg QD in subjects from China and selected countries including Brazil and South Korea with RA who have completed Period 1.

The study is designed to enroll approximately 322 subjects at approximately 50 study centers worldwide to meet scientific and regulatory objectives without enrolling an undue number of subjects in alignment with ethical considerations. Therefore, if the target number of subjects has been enrolled, there is a possibility that additional subjects in screening will not be enrolled.

The study duration will include a 35-day screening period; a 12-week randomized, double-blind, parallel-group, placebo controlled treatment period (Period 1); an open-label 52-week extension period (Period 2); and a 30-day follow-up period (call or visit).

Subjects who meet eligibility criteria will be randomized in a 1:1 ratio to one of two treatment groups. As indicated below, it is expected that approximately 222 subjects will enter the study from China and 100 subjects from other countries including Brazil and South Korea:

- Group 1: Upadacitinib 15 mg QD (N = 161; 111 from China) (Period 1) → Upadacitinib 15 mg QD (Period 2)
- Group 2: Placebo (N = 161; 111 from China) (Period 1) → Upadacitinib 15 mg QD (Period 2)

Randomization will be stratified by country and the Chinese population will be up to 80% of the total study population.

Subjects must have been on a stable dose of csDMARD(s) for  $\geq$  4 weeks prior to the first dose of study drug and must remain on a stable dose until Week 24; the csDMARD dose may be decreased only for safety reasons.

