**8.1.2.3      Study Drug Exposure**

Exposure to study drug will be summarized for the Safety Analysis Set for Period 1 alone as well as for Period 1 and Period 2 combined. The exposure to study drug (days) will be summarized with the mean, standard deviation, median, and range for each treatment group. The exposure to study drug is defined as the difference between the dates of the first and last doses of the study drug plus 1 day.

Study drug compliance will be summarized for each treatment group. The compliance is defined as the number of tablets taken (i.e., the difference between the number of tablets dispensed and the number of tablets returned) during the subject's participation divided by the number of tablets a subject is supposed to take each day times the length of time that the subject was in the Treatment Phase.

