##### **8.1.5.2.1 Treatment-Emergent Adverse Events (TEAE)**

AEs will be coded using MedDRA. A TEAE is defined as AE that began or worsened in severity after initiation of study drug.

AEs starting more than 30 days following the last dose of study drug will not be included in summaries of TEAEs. For subjects who continued into Period 2, AEs that are reported in Period 2 will be captured in the combined safety analysis of Period 1 and Period 2.

As a general safety summary, the number and percentage of subjects experiencing TEAEs will be summarized for each treatment group for the following AE categories:

- All AEs;
- All severe AEs;
- All reasonably possibly related AEs;
- All SAEs;
- Frequent AEs (reported in 2% of subjects or more in any treatment group);
- Frequent reasonably possibly related AEs (reported in 2% of subjects or more in any treatment group);
- Discontinuations due to AEs;
- Death.

Additional AEs may be considered for tabulation/summary based on recommendations from Clinical and Safety as deemed appropriate.

TEAEs will be summarized and presented by system organ classes (SOCs) and preferred terms (PTs) using MedDRA. The SOCs will be presented in alphabetical order, and the PTs will be presented in alphabetical order within each SOC.

TEAE will also be summarized by maximum severity and by maximum relationship.

The AEs of special interest (including but not limited to serious infection, opportunistic infection, herpes zoster, TB, gastrointestinal perforations, malignancies, adjudicated cardiovascular events (e.g., major adverse cardiovascular event [MACE]), lipid profile changes, anemia, neutropenia, lymphopenia, increased serum creatinine and renal dysfunction, hepatic events and increased hepatic transaminases, elevated CPK and non-cardiac, non-CNS embolic and thrombotic events) will be summarized. Event rate (per 100 patient years) for AEs of special interest will also be summarized for the combined safety analysis of Period 1 and Period 2.

---

All AEs leading to discontinuation of study drug will be presented in listing format. A listing by treatment group of TEAEs grouped by SOC and MedDRA preferred term with subject identification numbers will be generated.

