10.0 Safety Analysis

10.1 General Considerations

Safety analyses will be carried out using the Safety Analysis Set. There are two sets of planned safety analysis: safety analysis for Period 1 and long-term safety analysis.

Safety Analysis for Period 1

Standard safety analysis by the "as treated" treatment groups of upadacitinib 15 mg QD and the placebo groups will be performed on safety data in Period 1. No protocol-defined treatment switching will occur prior to the end of Period 1.

The standard safety analyses will include reporting of adverse events (AEs), laboratory and vital signs measurements. Frequency tables of subjects with treatment-emergent adverse events (TEAEs) by system organ class (SOC) and by preferred term (PT) as in the Medical Dictionary for Regulatory Activities (MedDRA) dictionary will be provided by treatment group. Mean changes from baseline in all continuous laboratory parameters and vital signs variables at each visit will be summarized by "as treated" treatment group. Frequency tables of subjects meeting criteria for potentially clinically significant vital sign values and for potentially clinically significant laboratory values will be provided by treatment group. Missing safety data will not be imputed.

Long-Term Safety Analysis

Long-term safety analyses for upadacitinib 15 mg QD include reporting of AE rate adjusted by cumulative exposure, mean change from baseline in laboratory parameters and vital sign variables, and frequency of potentially clinically significant laboratory and vital signs values. The treatment-emergent adverse event (TEAE) rate per 100 patient-years of exposure will be presented by actual treatment received at the time of AE (as described in Section 10.2.2). Listing of subjects with TEAEs by SOC and PT will be

provided. Mean changes from baseline in all continuous laboratory parameters and vital signs variables at each visit will be summarized by "as treated" treatment group sequences defined as follows (as described in Section 10.3.3 and Section 10.4.3). Frequency tables and listings of subjects meeting criteria for potentially clinically significant vital sign values and for potentially clinically significant laboratory values will be provided by actual treatment received at the time of event. Missing safety data will not be imputed.

"As treated" treatment group sequences:

1. upadacitinib 15 mg QD
2. Placebo → upadacitinib 15 mg QD

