10.2 Analysis of Adverse Events

A treatment-emergent Adverse Event (TEAE) is defined as an adverse event with an onset date that is after the first dose of study drug, and no more than 30 days of the drug after the last dose of study drug.

Events where the onset date is the same as the study drug start date are assumed to be treatment-emergent, unless the study drug start time and the adverse event start time are collected and the adverse event start time is prior to the study drug start time. If an incomplete onset date was collected for an adverse event, the event will be assumed to be treatment-emergent unless there is other evidence that confirms that the event was not treatment-emergent (e.g., the event end date was prior to the study drug start date).

Adverse event data will be presented by SOCs and PTs using MedDRA version 21.1 or most up to date version. All adverse event tables will be sorted in alphabetical order by SOC and PT.

10.2.1 Analysis of Adverse Events for Period 1

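### Long-term adverse event rates in SAP 10.2.2 count events up to 30 days after the last dose but divide by first-to-last-dose days, so numerator and denominator cover different time at risk

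*SAP*

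**What the plan says.** The two documents set the same outer limit for a treatment-emergent event. SAP 10.2 allows onset "no more than 30 days of the drug after the last dose of study drug", and Protocol 8.1.5.2.1 says "AEs starting more than 30 days following the last dose of study drug will not be included in summaries of TEAEs".

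SAP 10.2.2 then builds the long-term rate from that defined term: "the numerator of the overall rate will be the total number of TEAEs reported for the event", with repeat events in one subject all counted. On the other side of the fraction, "The denominator of the rates will be the total number of days exposed to upadacitinib 15 mg QD summed across all treated subjects", converted to years at 365.25 days. The SAP does not define exposure days in 8.1 or in 10.2.2. Protocol 8.1.2.3 does: "difference between the dates of the first and last doses of the study drug plus 1 day". Nothing in either document adds the 30 days to the denominator.

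Two further phrases bear on the numerator. SAP 10.2.2 introduces the analysis with "This includes TEAEs occurred under upadacitinib 15 mg QD exposure from subjects starting on upadacitinib 15 mg QD" (and from subjects who switch from placebo), and SAP 10.1 says the rate is presented "by actual treatment received at the time of AE". Neither states what happens to an event that starts after the last dose, when no study treatment is being taken.

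**The concern.** A rate per unit of time is interpretable when the events counted are those that could have arisen during the time counted. Here each finished subject can contribute events for up to 30 days longer than he or she contributes time. Those days are observed by design: Protocol 6.1.4 collects all adverse events until 30 days after study drug stops, and Protocol 5.1 plans a follow-up contact at about that point.

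Long-term safety is the first-named aim of Period 2, and these rates are its planned adverse event summary: overall, by system organ class and preferred term, and for each adverse event of special interest (SAP 10.2.2.1 to 10.2.2.3). At the Week 12 lock (SAP 4.4), continuing subjects have no post-treatment window yet; at the end of the study every subject may have one. Rates from the two locks would therefore carry different amounts of distortion.

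**Working it through.** The documents give no adverse event rate, patient-year total or bias figure, so there is no stated result to reproduce. The check is direct arithmetic.

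**Inputs**

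- Period 1: 12 weeks = 84 days (Protocol 5.1: "Period 1 is a 12-week, randomized, double-blind, parallel-group, placebo-controlled period"). Period 2: 52 weeks = 364 days (Protocol 5.1; SAP 4.2).
- Planned upadacitinib exposure D: 84 + 364 = 448 days for subjects on upadacitinib throughout, 364 days for placebo switchers.
- 161 subjects per arm (Protocol 5.1).
- Post-dose window: 30 days (SAP 10.2).
- Dropout: 10% (SAP 4.3), or 10% to 15% (SAP 9.1.2). The share of exposure completed by dropouts is not given; I assume a quarter to a half.
- f, the ratio of the event rate in the 30 days after stopping to the rate on drug: not given; assumed range 0 to 2.

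**1. Patient-years if all 322 complete**

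- Exposure: 161 × 448 + 161 × 364 = 130,732 days; ÷ 365.25 = 357.9 patient-years. Mean D = 130,732 / 322 = 406 days.
- Post-dose window: 322 × 30 = 9,660 days; ÷ 365.25 = 26.4 patient-years.
- Matched total: 384.4 patient-years.

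**2. SAP rate against a matched denominator: (D + 30) / D**

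This ratio does not depend on f, because the numerator is the same in both rates.

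- Upadacitinib throughout: 30/448 = 6.7% too high.
- Placebo switchers: 30/364 = 8.2% too high.
- Pooled: 9,660/130,732 = 7.4% too high. Equivalently, the fix multiplies each rate by 406/436 = 0.931.

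With dropout proportion d and dropouts completing share k of planned exposure, the pooled excess is 9,660 / [130,732 × (1 − d + dk)]:

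| d | k = 0.5 | k = 0.25 |
|---|---|---|
| 10% | 7.8% | 8.0% |
| 15% | 8.0% | 8.3% |

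**3. SAP rate against the on-drug rate: excess = 30f / D, with D = 406**

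| f | SAP rate relative to on-drug rate | Matched-denominator rate relative to on-drug rate, (406 + 30f)/436 |
|---|---|---|
| 0 | 0% | 6.9% lower |
| 0.5 | 3.7% higher | 3.4% lower |
| 1 | 7.4% higher | equal |
| 2 | 14.8% higher | 6.9% higher |

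**4. Week 12 lock, upadacitinib arm, Period 1 exposure only**

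Only discontinued subjects have a post-dose window. Assuming they stop at mid-period (42 days), the excess over a matched denominator is 30d / [84(1 − d) + 42d]:

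- d = 5%: 1.5/81.9 = 1.8%
- d = 10%: 3.0/79.8 = 3.8%
- d = 15%: 4.5/77.7 = 5.8%

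Period 2 exposure and discontinuations already accrued at that lock would alter these figures.

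**The case against.** The strongest objection is that the numerator may already be restricted. SAP 10.2.2 speaks of events occurring under upadacitinib exposure, and SAP 10.1 assigns events by the treatment being taken at onset. Read strictly, both exclude events after the last dose, and the fraction would then match. The reading is possible but not the better one. In context, the two phrases separate upadacitinib time from placebo time in subjects who switch, and the sentence that specifies the numerator uses the defined term without restriction. If exclusion were intended, it would need saying, because it departs from SAP 10.2.

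Other points on that side stand:

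- The quantity is labelled a rate per patient-years of study drug exposure, the numerator and denominator are both to be reported, and any error is upward, the cautious direction for safety.
- Serious events, deaths and events leading to discontinuation are also listed individually (SAP 10.2.2.4).
- The 26.4 patient-years assume that every subject is followed for 30 days. After premature discontinuation that contact depends on the subject's willingness (Protocol 5.1 and 5.4.1).
- If risk falls after stopping, adding off-drug days dilutes the on-drug rate, by up to 6.9% when no events occur in the window.

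These limit the size and weight of the point. They do not make the two windows agree.

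A reader might also infer more than the documents support:

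- *Every rate is overstated.* This is true of non-zero rates against a matched denominator. Against the on-drug rate, a category with no post-dose events is unaffected, and events leading to discontinuation of study drug would rarely start after the last dose.
- *The 7.4% is a ceiling.* It is the excess over the on-drug rate at f = 1. A higher off-drug rate gives more.
- *The bias exceeds 100% in early stoppers.* For someone stopping after four weeks, 30/28 is about 107%, but SAP 10.2.2 pools events and days over all treated subjects and plans no rate for early stoppers.
- *The denominator holds only days on drug.* Under Protocol 8.1.2.3, interruption days between first and last dose count as exposure, which pulls the rate slightly down.

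**Conclusion.** The mismatch is real on the operative definitions. At final analysis it makes the pooled long-term rates about 7% too high against a matched denominator: 7.4% with full planned follow-up, and 7.8% to 8.3% with 10% to 15% dropout under the assumed exit times. For the Week 12 lock, the Period 1 illustration gives 1.8% to 5.8%. How far the rates exceed the on-drug rate cannot be settled from the documents, because f is unknown; over the assumed range it is 0% to 14.8%.

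The figures rest on planned treatment lengths, all placebo subjects switching when no dropout is assumed, and 30 observed days after the last dose.

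The consequence is limited. A reader might fear that the safety comparison with placebo is affected. It is not: these rates are for upadacitinib alone, with no test or comparator, and the controlled comparison in SAP 10.2.1 uses Period 1 percentages of subjects. What is affected is the absolute level of the long-term rates and their comparability between the two locks. The change is worth making before the rates are produced, but nothing confirmatory depends on it.

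**What to change.** In SAP 10.2.2:

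- State that treatment-emergent events with onset after the last upadacitinib dose, within the 30-day window, count in the numerator.
- Run the denominator from the first upadacitinib dose to the earliest of last dose plus 30 days, last contact and data cut.
- Show the rate on first-to-last-dose exposure alongside, for comparison with other studies.

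In SAP 8.1, define exposure days, carrying over the Protocol 8.1.2.3 definition and making clear that interruption days are included.

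Limiting the numerator to first through last dose would also align the two windows with no change to the denominator, but it would drop post-dose events that the plan defines as treatment-emergent and collects. Extending the denominator keeps them.

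The cost is one derived variable and a footnote. Rates on the matched denominator will be about 7% lower (factor 0.931 with full follow-up) and should not be set beside exposure-based rates from other studies without that note. If risk falls after stopping, they will also slightly dilute the on-drug rate, which is why both versions should be shown.
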